## G) TRIAL DURATIONS

**INCLUSION PERIOD:** 5 years

**TRIAL TREATMENT PERIOD:** Treatment will be continued until radiographic disease progression. Treatment may also be terminated early by the investigator for any reason that would be beneficial to the patient, (e.g. unacceptable toxicity, intercurrent conditions that preclude continuation), or patient request.

**FOLLOW-UP:** 10 years per patient, from date of randomisation

**DURATION UNTIL PRIMARY ENDPOINT EVALUATION:**  
Approximately 15 months after inclusion of the last patient

**OVERALL TRIAL DURATION (INCLUDING FOLLOW-UP):** 15 years

## SCHEDULE OF VISITS AND ACTIVITIES

VISIT #	SCN	V1	V2	V3	V4	V5	V6	Vn (if <2y)	Vn (if > 2y)	EOT	LTFU
Days	D-28 – D0	D1	D30	D60	D120	D180	D240	Q120d	Q180d		Q180d
Written informed consent	X										
Inclusion / exclusion criteria	X	X									
Randomisation		X									
Study treatment ( according to IWRS )		X	X	X	X	X	X	X	X		
CLINICAL EXAMINATIONS											
Weight and height	X		X	X	X	X	X	X	X	X	
Complete clinical examination & vital signs	X		X	X	X	X	X	X	X	X	
ECOG performance status	X		X	X	X	X	X	X	X	X	X (b)
Collection of toxicities / AEs / symptoms	X	X	X	X	X	X	X	X	X	X	X (a)
Collection of concomitant therapies	X	X	X	X	X	X	X	X	X	X	X (b)
PARACLINICAL EXAMINATIONS											
Scanner (CT/MRI)	X (l)				X		X	X	X	X	X (b)
Bone scan	X (l)				X		X	X	X	X	X (b)
PCWG3 disease assessment	X				X		X	X	X	X	X (b)
Electrocardiogram (c)	X (c)			X (c)	X (c)	X (c)	X (c)	X (c)	X (c)	X (c)	
LABORATORY EXAMINATIONS											
Haematology (d)	X (e)		X	X	X	X	X	X	X	X	
Serum chemistry (f)	X (e)		X	X	X	X	X	X	X	X	
PSA, testosterone	X		X	X	X	X	X	X	X	X	X (b)
BIOLOGICAL SAMPLE COLLECTION											
Tumour biopsy (if available) (g)	X (h)									X (i)	
Blood samples – French sites only (g)		X	X	X	X					X (i)	
TRANSLATIONAL STUDY ON SARCOPENIA											
Abdominal circumference, body mass index	X		X	X	X	X	X	X	X	X	
Maximum handgrip strength (m)	X (m)		X (m)	X (m)	X (m)	X (m)	X (m)	X (m)	X (m)	X (m)	
GERIATRIC ASSESSMENT											
G8 screening test	X										
G-CODE	X				X		X	X	X	X	
CISR-G	X										
QUALITY OF LIFE ASSESSMENT											

UNICANCER Tumour Group: GETUG

Protocol n°: UC-GTG-2006

EudraCT n: 2020-003663-26

VISIT #	SCN	V1	V2	V3	V4	V5	V6	Vn (if <2y)	Vn (if > 2y)	EOT	LTFU
Days	D-28 – D0	D1	D30	D60	D120	D180	D240	Q120d	Q180d		Q180d
EORTC-QLQ-C30		X (k)			X		X	X	X	X	
EORTC-QLQ-PR25		X (k)			X		X	X	X	X	
BPI-SF		X (k)			X		X	X	X	X	X (b)
SURVIVAL STATUS											
Survival status											X (l)
Subsequent antineoplastic therapy											X (l)
Subsequent progression / relapse											X (l)

AE: Adverse event; BPI-SF: Brief Pain Inventory - Short Form; CISR-G: Cumulative Illness Score Rating-Geriatrics; CT: Computed tomography scan; D: Day(s); ECOG: Eastern Cooperative Oncology Group; EORTC-QLQ: European Organisation for Research and Treatment of Cancer – Quality of Life Questionnaire; EOT: End of treatment visit; G-CODE: Geriatric Core Dataset; IWRS: Interactive web response system; LTFU: Long-term follow-up visit; MRI: Magnetic resonance imaging; PCWG3: Prostate Cancer Working Group 3 ([Scher, 2016](#)); PSA: Prostate specific antigen; Q: Every; SCN: Screening period (up to 28 days prior to randomisation); V: Visit

- (a) Status of ongoing adverse events and/or new treatment-related adverse events
- (b) If patient discontinued study treatment for a reason other than radiographic disease progression, procedure is to be performed according to the protocol schedule until disease progression.
- (c) Mandatory at the screening visit, to be repeated at subsequent visits only in case of abnormal results or if clinically indicated by patient symptoms
- (d) Haematology: Haemoglobin, Haematocrit, Platelet count, Red blood cell count, White blood cell count (total and differential), Absolute neutrophil count, Lymphocytes
- (e) To be performed within 7 days prior to the first administration of study treatment
- (f) Serum chemistry: Alanine aminotransferase (ALAT), Albumin, Alkaline phosphatase, Aspartate aminotransferase (ASAT), Blood urea nitrogen, Calcium, Chloride, C-reactive protein, Creatinine (With estimated GFR [MDRD or CKI EPI method]), Direct Bilirubin (If total bilirubin is elevated above the upper limit of normal), Gamma-glutamyl transferase (GGT), Glucose, Lactate dehydrogenase, Magnesium, Phosphorus, Potassium, Sodium, Total Bilirubin (+ Direct Bilirubin if total bilirubin is elevated above the upper limit of normal), Total protein, Urea, Uric Acid
- (g) Optional: To be performed only for patients who provide additional informed consent to translational analysis
- (h) Archived Formalin fixed / paraffin embedded (FFPE) biopsy material obtained at time of diagnosis as part of the standard medical care will be collected at study entry.
- (i) At the time of disease progression, if medically feasible.
- (j) This information may be collected during onsite visits (as part of patients continued treatment at the site), via communication with the patients treating physician or via telephone contact with the patient.
- (k) The questionnaires must be completed before the initiation of treatment.
- (l) Paraclinical examination (CT scan or MRI and bone scan) to be performed within 12 weeks prior to randomization, but we strongly recommend that baseline imaging be performed within 28 days prior to randomization.
- (m) handgrip strength should be measured twice at each visit.

## 1. INTRODUCTION

### 1.1. Background information

#### 1.1.1. *Disease/pathology epidemiology*

Prostate cancer is the most commonly occurring cancer in men. In Europe approximately 450,000 new cases are diagnosed per year and prostate cancer remains the third-leading cause of cancer mortality in men, with approximately 107,000 deaths in 2018 ([Ferlay, 2018](#)). Although metastases are detected at diagnosis in only about 10% of cases in Europe, *de novo* metastatic (M1) prostate cancer is responsible for most of these deaths ([Patrikidou, 2014](#)).

#### 1.1.2. *Prognosis*

The 5-year survival rate for patients diagnosed with M1 prostate cancer is 31%, compared with a survival rate approaching 100% for cancers diagnosed at a local or regional stage ([Cancer Facts & Figures 2020](#)).

#### 1.1.3. *Investigational medicinal products (IMP)*

Darolutamide (or N-((S)-1-(3-(3-Chloro-4-cyanophenyl)-1H-pyrazol-1-yl)propan-2-yl)-5-(1-hydroxyethyl)-1H-pyrazole-3-carboxamide), is a novel nonsteroidal antagonist of the androgen receptor (AR), developed by the Orion Corporation Orion Pharma (Orion) and Bayer Healthcare.

Darolutamide, which is structurally distinct compared to other anti-androgens, potentially inhibits androgen binding to AR and retains antagonistic properties in cells expressing increased AR levels. Darolutamide diminishes AR-signalling by inhibiting testosterone-mediated nuclear localization of AR.

Darolutamide shows anti-androgenic and anti-tumour activity in in vitro and in vivo models of castrate resistant prostate cancer (CRPC).

Darolutamide is a 1:1 mixture of two pharmacologically active diastereomers: (S,R)-darolutamide and (S,S)-darolutamide which shows no major differences in pharmacological activity in vitro. The major metabolite keto-darolutamide has similar high binding affinity for the AR and exhibits comparable activity in in vitro assays.

Darolutamide is provided as 300 mg tablets.

The product is currently approved by all major regulatory authorities including the United States of America, Food and Drug Administration (FDA), the Japanese Pharmaceuticals and Medical Devices Agency (PMDA) and the European Medicines Agency (EMA) for the treatment of men with non-metastatic CRPC and is in clinical development in a phase 3 trial in metastatic hormone-sensitive prostate cancer (HSPC). A comprehensive set of primary and secondary pharmacodynamics, safety pharmacology, pharmacokinetics (PK) and metabolism, and toxicology studies was conducted to demonstrate the non-clinical safety and efficacy of darolutamide.

Until now, darolutamide has been studied in 12 company-sponsored clinical studies, of which six studies were conducted in prostate cancer patients and six studies were conducted in non-cancer subjects i.e. healthy volunteers and subjects with renal or hepatic impairment: a first-in-man (FIM) study with a Phase II cohort expansion (Study 17829 ARADES); a long-term safety extension study for the FIM study (Study 18035 ARADES EXT); a bioavailability study (Study 17830 ARAFOR); a mass balance and bioavailability study in healthy male subjects (Study 17831 ARIADME); a study to investigate the safety, tolerability, and PK of darolutamide in Japanese subjects with metastatic

CRPC (Study 17719); a study to investigate the PK, safety and tolerability in subjects with hepatic impairment, renal impairment, and normal hepatic and renal function (Study 17721); a Phase I Drug-Drug interaction (DDI) study in healthy male and female subjects (Study 17723) to investigate the effect of darolutamide on the PK of a probe substrate for the transporters BCRP, OATP1B1, OATP1B3, and OAT3; a Phase I DDI study in healthy male subjects (Study 17726) investigating the influence of CYP3A4/P-gp mediating agents on the PK of darolutamide, its diastereomers and major metabolite; and another Phase I DDI study in healthy male subjects (Study 18860) to assess the effect of darolutamide on the PK of probe substrates of CYP3A4 and P-gp; and a Phase I, randomised, placebo-controlled, open-label, three period crossover, study to investigate the effect of darolutamide and enzalutamide on cerebral blood flow in healthy male volunteers (Study 18426). In addition, it is currently being studied in two randomised double blind Phase III studies; in men with non-metastatic CRPC and a PSA doubling time of 10 months or less (ARAMIS 17712) and in men with metastatic HSPC (ARASENS 17777). The results of clinical studies indicate that darolutamide is well-tolerated, and demonstrates anti-tumour efficacy in patients with CRPC.

Refer to the current version of the darolutamide Investigator Brochure for a complete summary of non-clinical and clinical data including safety, efficacy, and pharmacokinetics data.

## 1.2. Trial rationale

For more than 7 decades, men with metastatic HSPC were treated with androgen deprivation therapy (ADT) alone, with no meaningful progress until 2013, when the French GETUG-15 trial showed that combining ADT with docetaxel improved progression-free survival (PFS) (Hazard ratio [HR]: 0.72, 95% confidence interval [CI]: 0.57–0.91;  $p=0.005$ ), but not overall survival (OS) ([Gravis, 2013](#); [Gravis, 2016](#)). Subsequently, two larger Phase III trials, CHAARTED and STAMPEDE showed that ADT + docetaxel also improved OS compared to ADT alone (median OS: 57.6 vs 47.2 months [HR: 0.72, 95%CI: 0.59-0.89,  $p=0.0018$ ] and 65 vs. 43 months [HR: 0.73, 95%CI: 0.59–0.89;  $p=0.002$ ] respectively) ([Sweeney, 2015](#); [James, 2016](#)).

More recently, the combination of ADT with next-generation AR axis-targeted agents has also been demonstrated to confer a survival benefit to M1 prostate cancer patients, compared to ADT alone.

The LATITUDE and STAMPEDE trials compared the efficacy of combining abiraterone and prednisone with ADT. In the LATITUDE trial median OS was 53.3 with abiraterone, prednisone and ADT compared with 36.5 months with ADT alone (HR: 0.66, 95%CI: 0.56-0.78,  $p<0.0001$ ) ([Fizazi, 2017](#)). The STAMPEDE trial also found a significant OS benefit in favour of the combination (HR: 0.61, 95%CI: 0.49-0.75) ([James, 2017](#)). Similar OS findings have also been reported for combinations of enzalutamide + ADT (ENZAMET trial: HR: 0.67, 95%CI: 0.52-0.86,  $p=0.002$ ) and apalutamide + ADT (AXIS trial: HR: 0.67, 95%CI: 0.51-0.89,  $p=0.005$ ) compared with ADT alone ([Davis 2019](#), [Chi 2019](#)).

The ongoing PEACE-1 trial is currently investigating whether adding abiraterone or local radiotherapy to men receiving ADT + docetaxel can further improve OS beyond that seen with the doublet therapy: the planned accrual of 1173 men was completed in December 2018 and first read outs are expected in 2021.

[figure not shown]
### The PEACE-6 umbrella programme

Previous trials of M1 prostate cancer treatment combinations described above were open to all comers. Our hypothesis is that tailoring treatment based on clinical and molecular characteristics is now required to keep improving outcomes.

The PEACE 6 programme represents a collaborative network of investigators from 14 European countries (Belgium, France, Germany, Ireland, Italy, The Netherlands, Norway, Poland, Portugal, Romania, Slovakia, Spain, Sweden, and Switzerland). Under the PEACE 6 umbrella program, M1 prostate cancer patients will be oriented to a specific randomised comparative trial of combination therapy versus standard of care (SOC) according to patient and disease characteristics. Four trials have been defined initially and patients will be allocated to one of these trials according to the following ranking:

1. PEACE-6 Oligo: Will evaluate the addition of metastases-directed radiotherapy to SOC in patients with oligo-metastatic prostate cancer: approximately 30% of patients;
2. PEACE-6 Vulnerable: Will evaluate the combination of darolutamide with SOC in “unfi” elderly M1 prostate cancer patients (defined by geriatric scales): approximately 20% of patients;
3. PEACE-6 PARPi-IO: Will evaluate the combination of a PD-1 inhibitor plus a PARP inhibitor with SOC in M1 prostate patients with either homologous recombination deficiency positive (HRD+), microsatellite instability (MSI-high), or cdk12-/- cancers: approximately 15% of patients;
4. PEACE-6 PSMA: Will evaluate the benefit of prostate-specific membrane antigen (PSMA) targeted therapy for M1 prostate cancer patients who do not fit in previous subgroups and who respond poorly to SOC (i.e. PSA >0.1 ng/mL, 6-8 months after initiation of systemic treatment, with no evidence of cancer progression, including no rising PSA): approximately 35% of patients.

Additional trials may be added at a later date according to changes in the treatment landscape and state of the art.

**Figure 1. Schematic of the PEACE 6 programme of clinical trials in *de novo* metastatic prostate cancer**

## PEACE-6 Vulnerable

The health status of men over 70 years old can vary widely. Some elderly patients may have no comorbidity and remain autonomous, while others must deal with polypharmacy, severe comorbidities, or impaired cognitive or physical function. The former are usually eligible to receive standard treatments but for the latter group of men, who are usually excluded from clinical trials, the best treatment options remains to be tested. With the aging of the European population, we believe that clinical trials with the specific aim of optimizing treatments in the unfit population are a top priority.

In recent years, several attempts have been made to define frailty, but so far there is no consensus on how to identify this population. Balducci defined frailty as a condition of dependence and vulnerability, which is reflected in abnormalities in one or more activities of daily living (ADL), severe comorbidity and cognitive deterioration ([Balducci, 2000](#)).

The current SOC for vulnerable men with M1 prostate cancer remains ADT alone. This subgroup is unfit to receive currently available systemic ADT combination regimen: docetaxel because of its multiple side effects; abiraterone due to the need for concomitant steroids, related muscle loss and other side effects; and enzalutamide or apalutamide due to their central nervous system-related adverse events including increased risk of falls and fractures and potential for important drug-drug interactions. Moreover, both abiraterone and enzalutamide significantly increase the incidence of cardiovascular events.

Darolutamide is a next-generation AR antagonist with a different chemical structure to apalutamide and enzalutamide. It was previously studied in two Phase I-II trials (ARADES and ARAFOR) and both trials supported strong activity and minimal toxicity (with no clear drug-related side effect detected) in patients with various stages of metastatic CRPC ([Fizazi, 2014](#); [Massard, 2016](#)).

Darolutamide has low penetration of the blood-brain barrier, a property that may reduce the risk of fatigue and seizure, and does not require concomitant steroids. Darolutamide does not bind significantly to cytochrome CYP 3A4. Thus, it is hypothesized that combining ADT with darolutamide will improve patients' outcomes compared to ADT alone, with an acceptable toxicity. Indeed, darolutamide + ADT was recently shown to improve metastases-free survival over ADT alone in patients with non-metastatic CRPC (median: 40.4 vs 18.4 months, HR: 0.41, 95%CI: 0.34-0.50,  $p < 0.001$ ). In the final analysis of the ARAMIS trial, darolutamide with ADT demonstrated a significant decrease in risk of death by 31% vs ADT alone (HR 0.69,  $p = 0.003$ ) and a remarkable safety profile, with almost no significant side effects compared to ADT alone ([Fizazi, 2019](#)). This very favourable efficacy/safety profile makes darolutamide a perfect candidate for this vulnerable M1 prostate cancer population.

PEACE-6 Vulnerable will compare the efficacy and safety of ADT + darolutamide versus ADT + placebo in this "frail" (defined by geriatric scales) elderly castration-naïve M1 prostate cancer population.

### 1.3. Justification for the therapeutic regimens and treatment durations

Previous Phase 2 and Phase 3 studies have demonstrated that darolutamide administered orally (*per os*, po) at a dose of 600 mg twice a day (b.i.d) to patients with non-metastatic CRPC improved OS with a good safety profile ([Fizazi, 2019](#)).

In this trial, darolutamide 600 mg, or a placebo control will be administered po, b.i.d to patients with castration-naïve prostate cancer in combination with standard ADT. Treatment will be continued until disease progression according to Prostate Cancer Working Group 3 (PCWG3) criteria ([Scher, 2016](#)).

Treatment may also be terminated at the initiative of either the patient or the investigator for any reason that would be beneficial to the patient, including: unacceptable toxicity, intercurrent conditions that preclude continuation of treatment, or patient request.

## 1.4. Potential risks and benefits

### 1.4.1. *Known potential risks*

Foreseeable risks of study participation therapy include a lack of response to treatment, and potential side effects related to darolutamide as outlined in the Investigator's Brochure.

The overall safety profile of darolutamide is based on data from 1508 patients of whom 954 received at least one dose of darolutamide in the Phase 3 Study 17712 (ARAMIS). The incidence of treatment emergent adverse events (TEAE) leading to permanent discontinuation of study treatment was comparable in both darolutamide (8.9%) and placebo (8.7%) treatment arms. The adverse drug reactions (ADRs) observed with darolutamide are rash, pain in extremity (common) and fatigue (very common). Laboratory test abnormalities related to darolutamide treatment and reported more frequently in darolutamide-treated patients compared to placebo-treated patients in the ARAMIS study were neutrophil count decreased, bilirubin increased, and aspartate aminotransferase (ASAT) increased.

As darolutamide shares a mode of action with the ADT and with the novel anti-androgens, the key risks associated with ADT and with the novel anti-androgens such as osteoporosis/fractures, decrease in lean body weight/sarcopenia, insulin resistance, dyslipidaemia and cerebrovascular disorders are considered as potential risks of darolutamide.

The primary endpoint of the study is radiographic progression-free survival (rPFS). Measurement of this endpoint requires a regular evaluation of the disease by computed tomography (CT) scan, or magnetic resonance imaging (MRI) and bone scan. Radiographic exams are generally performed at 4-12 month intervals or to confirm a suspected evolution of the disease.

The risk associated with radiographic examination are those associated with an increased exposure to radiation.

### 1.4.2. *Known potential benefits*

The benefit of participation in the trial is access to a potentially efficacious experimental combination which has been shown to provide a better survival rate than current standard of care in similar settings (see Section 1.2).

## 1.5. Trial population

The trial population is to be composed of adult men, diagnosed with castration-naïve *de novo* metastatic prostate cancer, and who are ineligible to receive currently available systemic ADT combination regimen (docetaxel, abiraterone, or enzalutamide) and are considered as frail (defined by standard geriatric scales).

## 2. TRIAL OBJECTIVES

### 2.1. Primary objective

To compare the efficacy of ADT + darolutamide vs ADT + placebo in terms of radiographic progression-free survival in patients with castration-naïve *de novo* metastatic prostate cancer with vulnerable functional ability and not elected for docetaxel or other androgen receptor pathway inhibitors.

### 2.2. Secondary objective(s)

The key secondary objectives of PEACE-6 Vulnerable are:

- To assess the efficacy of ADT + darolutamide vs ADT + placebo in terms of:
  - Castration-resistant prostate cancer-free survival
  - Clinical progression-free survival (cPFS)
  - Overall survival
- To assess the safety profile of the ADT + darolutamide combination.

Other secondary objectives:

- Time to worsening in prostate cancer-related urinary symptoms
- Time to next symptomatic skeletal event
- Prostate specific antigen (PSA) response
- Prostate cancer-specific survival
- To assess the effect of ADT + darolutamide on subsequent lines of therapy
- To evaluate the evolution of quality of life and geriatric status in individuals during the treatment period
- To evaluate the impact of sarcopenia on survival and treatment response.

### 2.3. Exploratory objective(s)

- To identify the oncogenic drivers of *de novo* metastatic prostate cancer

## 3. TRIAL DESIGN AND ENDPOINTS

### 3.1. Description of the trial design

This is a Phase III, international, multicentre, randomised, double-blinded placebo controlled trial, evaluating the efficacy and safety of ADT +/- darolutamide in vulnerable men with castration-naïve *de novo* metastatic prostate cancer.

## 3.2. Trial Endpoints

### 3.2.1. Primary endpoint

Radiographic progression-free survival, defined as time from randomisation to radiographic progression as assessed by the investigator according to PCWG3 criteria ([Scher, 2016](#); Appendix 3), or death, whichever occurs first.

*According to the PCWG3 recommendations; radiographic progression is defined as either the appearance of two or more new bone lesions on bone scan or a nodal or visceral progression according to Response Evaluation Criteria in Solid Tumours version 1.1 (RECIST v1.1; [Eisenhauer, 2009](#)). The date of radiographic progression will be the date of the first reported event meeting the above definition (see Appendix 3 & Appendix 4 for further details).*

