#### 2. Disease outcomes:

##### Radiographic progression

Radiographic progression is defined as either:

- a) A nodal or visceral progression according to RECIST v1.1 (Appendix 4):
  - **Target lesions:** At least a 20% increase in the sum of diameters of target lesions, taking as reference the lowest value (nadir) obtained during the trial (this includes the baseline sum if that is the lowest on trial). In addition to the relative increase of 20%, the sum must also demonstrate an absolute increase of at least 5 mm.  
  
Lymph nodes must have grown by at least 5mm in the short axis from baseline or nadir and be  $\geq 1.0$  cm in the short axis to be considered to have progressed.  
  
**Warning:** when a progression is recorded with respect to the nadir but there is a response with respect to baseline, progression must be considered.
  - **Non-target lesions:** Unequivocal progression of existing non-target lesions.
  - **New lesions:** The appearance of one or more new lesions is also considered progression).

- b) The appearance of two or more new bone lesions on a bone scan.

**Note:** Results should be confirmed by a second scan at least 6 weeks later. In this case the date of progression will be considered as the date of the initial post-treatment scan, when the first two new lesions were documented.

The appearance of a single new bone lesion will not be considered as radiographic progression. The patient may receive local stereotactic body radiation therapy (SBRT) to the new bone lesion but no alteration should be made to the study treatment before confirmation of radiographic progression.

The date of radiographic progression will be the date of progression as per the above definition.

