**If yes, indicate the total number of NEW lesions compared to Baseline Scan**

(please select one)

☐ 0 ☐ 1 ☐ 2 ☐ 3 ☐ 4 ☐ 5 ☐ >5

*Note: Presence of new lesions at this time does not confirm progression*

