**1. Are there 2 or more new lesions compared to the D120 scan?**

☐ Yes ☐ No

*If "Yes", proceed to question 2*

*If "No", the patient does not have radiographic progression by bone scan*

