**3A. Were there 2 or more new lesions at the D120 SCAN compared to the BASELINE SCAN?**

☐ Yes ☐ No

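### Bone progression in the primary endpoint is defined inconsistently: two new lesions at D120 that persist are an event under Section 3.2.1 and Appendix 3, but not under Appendix 13

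*Protocol*

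**What the plan says.** Section 3.2.1 makes rPFS investigator-assessed by PCWG3 criteria. On bone it states that "radiographic progression is defined as either the appearance of two or more new bone lesions on bone scan", and on timing: "The date of radiographic progression will be the date of the first reported event meeting the above definition". It points to Appendices 3 and 4 for details and does not mention Appendix 13. The protocol summary repeats the bone definition without citing an appendix.

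Appendix 3, under radiographic progression, has the same two-lesion criterion but adds a note: "Results should be confirmed by a second scan at least 6 weeks later". On confirmation, "the date of progression will be considered as the date of the initial post-treatment scan, when the first two new lesions were documented". It asks for no lesions beyond the first two. In its baseline section, Appendix 3 also recommends the bone scan forms of Appendix 13, in a form adapted to this trial.

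Appendix 13 works differently. The D120 form warns: "Presence of new lesions at this time does not confirm progression". The form for later scans opens with "Are there 2 or more new lesions compared to the D120 scan"; if the answer is no, "the patient does not have radiographic progression by bone scan". If the answer is yes and this is the first scan after D120, it asks "Were there 2 or more new lesions at the D120 SCAN compared to the BASELINE SCAN". For later scans it asks whether two or more lesions new since D120 are confirmed. It gives no rule for dating the event.

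**The concern.** Whether a patient has had a primary-endpoint event should not depend on which page of the protocol the investigator has open. The call is made at about 100 planned sites. It feeds the 138-event interim and the 197-event final analysis, and radiographic progression also ends study treatment. If sites follow different texts, identical scans give different rPFS times.

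The problem may also be hard to undo. Section 6.1 schedules imaging until documented radiographic progression, and Sections 7.4.1 and 7.5.1 continue it off treatment only for patients who stopped for another reason. A patient called progressed on a single D120 scan may therefore have no later protocol scan, which is what both appendices need to classify him. About 115 of 300 patients had been enrolled at the current amendment.

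**Working it through.** **1. The plan's own figure.** Inputs from Section 10.1: HR 0.65, two-sided 0.05, power 85%, 1:1.
- Schoenfeld: 4 × (1.960 + 1.036)² / (ln 0.65)² = 35.9 / 0.1856, or 194 events.
- Freedman: (1.960 + 1.036)² × (1.65 / 0.35)² = 8.98 × 22.2, or 200 events.
- Power at 197 events: √197 / 2 × 0.4308 = 3.023. Less 1.960 this gives 85.6%; less the final boundary of 2.0 it gives 84.7%.

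The 197 events reproduce, so the sample size is not in dispute.

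**2. The texts side by side.** Bone component only, with no death and no nodal or visceral progression:

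| Bone scans | 3.2.1 and summary, read literally | Appendix 3 | Appendix 13 |
|---|---|---|---|
| Two new lesions at D120, persisting, none added | Event, D120 | Event, D120 | No event |
| Two new lesions at D120, not confirmed later | Event, D120 | No event | No event |
| Two new lesions at D120, two or more further on next scan | Event, D120 | Event, D120 | Event, no date stated |

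The scheduled D240 scan comes about 17 weeks after D120 (120 / 7), so it can serve as the Appendix 3 confirmation. Row 1 is the direct contradiction: question 1 of the later form is answered no, and the form then rules out bone progression. Row 2 separates only the literal reading of 3.2.1 from the two appendices. In row 3 all texts agree that there is an event.

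**3. How many patients.** The protocol gives no rate of new bone lesions at D120. Assume 5% to 15%: 0.05 × 300 = 15 and 0.15 × 300 = 45, which is 15/197 = 7.6% to 45/197 = 22.8% of the planned events. This bounds the patients exposed at D120. Row 3 patients are events whichever text is used, as are patients with concurrent nodal or visceral progression.

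For orientation, take the planned exponential medians and D120 = 120 / 30.4375 = 3.94 months:
- Control: 1 − 2^(−3.94/12) = 0.204, × 150 = 30.5.
- Experimental: median 12/0.65 = 18.46 months; 1 − 2^(−3.94/18.46) = 0.138, × 150 = 20.6.
- Total: about 51 rPFS events of every kind by D120, or 26% of 197, before drop-out. The bone share is not given.

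**4. Illustration of scale.** Trials were simulated (1,000 per scenario) with the planned medians, the Section 10.1 accrual table, drop-out hazard 0.014 taken as monthly, an unstratified log-rank test at the 197th event and boundary Z = 2.0. A share f of each arm, if event-free at D120, was given an event there although the disease had not progressed.

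| f (assumed) | Power | Average HR |
|---|---|---|
| 0 | 85% | 0.64 |
| 5% | 81% | 0.66 |
| 10% | 74% | 0.68 |
| 15% | 70% | 0.69 |

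The simulation error is 1.1 to 1.4 percentage points. This is an extreme case: every site follows the literal 3.2.1, and every affected lesion is not progression.

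**The case against.** Section 3.2.1 cites PCWG3 and sends the reader to Appendix 3, so it can fairly be read as the short form and Appendix 3 as the detail. Dating at the first reported event fits Appendix 3's back-dating. The D120 warning in Appendix 13 also fits Appendix 3, since both need a later scan. The Appendix 13 forms are only recommended, and 3.2.1 does not cite them. All of this stands. A reader might infer three mutually incompatible definitions, but the documents do not support that: the firm conflict is Appendix 13's demand for further lesions against Appendix 3. That conflict remains, because Appendix 3 itself recommends the forms that contradict it and no text says which prevails.

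Other inferences go too far:
- **Bone is the main component of rPFS.** The protocol gives no split of events into bone, soft tissue and death.
- **All 15 to 45 patients would change status or be re-dated by months.** Many would be events under every text, and Appendix 13 states no date from which a shift could be measured.
- **The comparison is biased towards one arm.** The trial is double-blind, and nothing in the protocol points to different misclassification by arm; the risk is dilution.
- **The independent review uses a different rule.** Its charter is a separate document and is not shown.

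**Conclusion.** The concern holds in limited form. Appendix 3 and Appendix 13 classify two persisting D120 lesions with none added in opposite ways, and 3.2.1 and the summary are silent on confirmation. Two lesions that are not confirmed later are an event only if 3.2.1 is read literally. This is a contradiction in the primary-endpoint rule that investigators apply at site, not detail left to a statistical analysis plan. Table 5 does not settle unconfirmed bone progression either. CRPC-free survival takes over the radiographic definition from Appendix 3 and inherits the problem.

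The number of affected patients is unknown. The range of 15 to 45 rests wholly on the assumed 5% to 15% and is an upper bound on exposure at D120. The simulated power loss rests on the further assumption that such lesions are not progression, and shows scale only. No figure in the sample size section changes.

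**What to change.** Reconcile Section 3.2.1, the summary, Appendix 3 and the Appendix 13 forms to one bone-progression rule for the endpoint. It should state:
- the reference scan;
- the confirmation required;
- the event date;
- the handling of lesions that are never confirmed, including when no later scan exists.

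Use that rule for the investigator-based primary derivation, for counting the 138 and 197 events, and for the independent review. The text on treating until radiographic progression must be reconciled with it. Which rule is right is for the sponsor and investigators to decide.

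Re-derive existing calls where later scans exist, and state in advance how patients whose imaging stopped after an unconfirmed call will be analysed. This should be settled before the interim analysis.

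The cost is wording in four places and a partial re-derivation. Some earlier calls may not be recoverable, and the timing of the 138th and 197th events may shift slightly.
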